8.2. Safety Assessments

Planned time points for all safety assessments are provided in the SoA. Unscheduled clinical laboratory measurements may be obtained at any time during the study to assess any perceived safety concerns.

8.2.1. Physical Examinations

A complete physical examination will include, at a minimum, assessments of the cardiovascular, respiratory, gastrointestinal, and neurological systems.

Investigators should pay special attention to clinical signs related to previous serious illnesses.

8.2.2. Vital Signs

Vital signs will be measured with the participant in a seated or supine position after 5 minutes of rest and will include temperature (tympanic, or axillary), systolic and diastolic blood pressure, and pulse rate, only performed at screening.

8.2.3. Clinical Safety Laboratory Assessments

See [Appendix 2](#) for the list of clinical safety laboratory tests to be performed at screening visit for eligibility purpose except pregnancy test.

All protocol-required laboratory assessments, as defined in [Appendix 2](#), must be conducted in accordance with the [SoA](#) for timing and frequency.

If laboratory values from non-protocol-specified laboratory assessments performed at the institution's local laboratory require a change in participant management or are considered clinically significant by the investigator (eg, SAE or AE or dose modification), then the results must be recorded in the CRF.

8.2.4. Pregnancy Testing

Pregnancy tests may be urine or serum tests, but must have a sensitivity of at least 25 mIU/mL. Pregnancy tests will be performed in WOCBP at the times listed in the [SoA](#). Following a negative pregnancy test result at screening, appropriate contraception must be commenced and a second negative pregnancy test result will be required at the baseline visit prior the participant's receiving the investigational products. Pregnancy tests will also be done whenever 1 menstrual cycle is missed during the active treatment period (or when potential pregnancy is otherwise suspected) and at the end of the study. Pregnancy tests may also be repeated if requested by institutional review boards (IRBs)/ethics committees (ECs) or if required by local regulations. If a urine test cannot be confirmed as negative (eg, an ambiguous result), a serum pregnancy test is required. In such cases, the participant must be excluded if the serum pregnancy result is positive.

8.2.5. Photography

Photographs of target lesions will be obtained at Baseline/Day 1, Day 8 and Day 15/Early discontinuation. Photographs will be taken by local standard procedures. Photographs will not be evaluated as an endpoint, but will be referred as needed, such as incident of significant AE. Only for participants who consent, photographs will be utilized for illustrative purposes.

8.3. Adverse Events and Serious Adverse Events

The definitions of an AE and an SAE can be found in [Appendix 3](#).

AEs will be reported by the participant (or, when appropriate, by a caregiver, surrogate, or the participant's legally authorized representative).

The investigator and any qualified designees are responsible for detecting, documenting, and recording events that meet the definition of an AE or SAE and remain responsible to pursue and obtain adequate information both to determine the outcome and to assess whether it meets the criteria for classification as an SAE or that caused the participant to discontinue the study (see [Section 7](#)).

In addition, the investigator may be requested by Pfizer Safety to obtain specific follow-up information in an expedited fashion.

8.3.1. Time Period and Frequency for Collecting AE and SAE Information

The time period for actively eliciting and collecting AEs and SAEs (“active collection period”) for each participant begins from the time the participant provides informed consent, which is obtained before the participant’s participation in the study (ie, before undergoing any study-related procedure and/or receiving investigational products), through and including a minimum of 28 calendar days, except as indicated below, after the last administration of the investigational products.

For participants who are screen failures, the active collection period ends when screen failure status is determined.

Medical occurrences that begin before the start of study intervention but after obtaining informed consent will be recorded on the Medical History/Current Medical Conditions section of the CRF, not the AE section.

Follow-up by the investigator continues throughout and after the active collection period and until the event or its sequelae resolve or stabilize at a level acceptable to the investigator, and Pfizer concurs with that assessment.

Investigators are not obligated to actively seek AEs or SAEs after conclusion of the study participation. However, if the investigator learns of any SAE, including a death, at any time after a participant has been discharged from the study, and he/she considers the event to be reasonably related to the study intervention or study participation, the investigator must promptly notify the sponsor.

8.3.1.1. Reporting SAEs to Pfizer Safety

All SAEs occurring in a participant during the active collection period are reported to Pfizer Safety on the CT SAE Report Form immediately and under no circumstance should this exceed 24 hours, as indicated in Appendix 3. The investigator will submit any updated SAE data to the sponsor within 24 hours of it being available.

SAEs occurring in a participant after the active collection period has ended are reported to Pfizer Safety if the investigator becomes aware of them; at a minimum, all SAEs that the investigator believes have at least a reasonable possibility of being related to investigational products must be reported to Pfizer Safety.

8.3.1.2. Recording Nonserious AEs and SAEs on the CRF

During the active collection period, both nonserious AEs and SAEs are recorded on the CRF.

8.3.2. Method of Detecting AEs and SAEs

The method of recording, evaluating, and assessing causality of AEs and SAEs and the procedures for completing and transmitting SAE reports are provided in Appendix 3.

Care will be taken not to introduce bias when detecting AEs and/or SAEs. Open-ended and nonleading verbal questioning of the participant is the preferred method to inquire about AE occurrences.

8.3.3. Follow-up of AEs and SAEs

After the initial AE/SAE report, the investigator is required to proactively follow each participant at subsequent visits/contacts. For each event, the investigator must pursue and obtain adequate information until resolution, stabilization, the event is otherwise explained, or the participant is lost to follow-up (as defined in Section 7.3).

In general, follow-up information will include a description of the event in sufficient detail to allow for a complete medical assessment of the case and independent determination of possible causality. Any information relevant to the event, such as concomitant medications and illnesses, must be provided. In the case of a participant death, a summary of available autopsy findings must be submitted as soon as possible to Pfizer Safety.

Further information on follow-up procedures is given in Appendix 3.

8.3.4. Regulatory Reporting Requirements for SAEs

Prompt notification by the investigator to the sponsor of an SAE is essential so that legal obligations and ethical responsibilities towards the safety of participants and the safety of a study intervention under clinical investigation are met.

The sponsor has a legal responsibility to notify both the local regulatory authority and other regulatory agencies about the safety of a study intervention under clinical investigation. The sponsor will comply with country-specific regulatory requirements relating to safety reporting to the regulatory authority, IRBs/ECs, and investigators.

Investigator safety reports must be prepared for suspected unexpected serious adverse reactions (SUSARs) according to local regulatory requirements and sponsor policy and forwarded to investigators as necessary.

An investigator who receives an investigator safety report describing an SAE or other specific safety information (eg, summary or listing of SAEs) from the sponsor will review and then file it along with the IB and will notify the IRB/EC, if appropriate according to local requirements.

8.3.5. Exposure During Pregnancy or Breastfeeding, and Occupational Exposure

Exposure to the investigational products under study during pregnancy or breastfeeding and occupational exposure are reportable to Pfizer Safety within 24 hours of investigator awareness.

8.3.5.1. Exposure During Pregnancy

Details of all pregnancies in female participants will be collected after the start of study intervention and until the end of the active collection period.

If a pregnancy is reported, the investigator should inform the sponsor within 24 hours of learning of the pregnancy and should follow the procedures outlined in Appendix 4.

Abnormal pregnancy outcomes (eg, spontaneous abortion, fetal death, stillbirth, congenital anomalies, ectopic pregnancy) are considered SAEs.

8.3.5.2. Exposure During Breastfeeding

Scenarios of exposure during breastfeeding must be reported, irrespective of the presence of an associated SAE, to Pfizer Safety within 24 hours of the investigator's awareness, using the CT SAE Report Form. An exposure during breastfeeding report is not created when a Pfizer drug specifically approved for use in breastfeeding women (eg, vitamins) is administered in accord with authorized use. However, if the infant experiences an SAE associated with such a drug's administration, the SAE is reported together with the exposure during breastfeeding.

8.3.5.3. Occupational Exposure

An occupational exposure occurs when, during the performance of job duties, a person (whether a healthcare professional or otherwise) gets in unplanned direct contact with the product, which may or may not lead to the occurrence of an AE.

An occupational exposure is reported to Pfizer Safety within 24 hours of the investigator's awareness, using the CT SAE Report Form, regardless of whether there is an associated SAE. Since the information does not pertain to a participant enrolled in the study, the information is not recorded on a CRF; however, a copy of the completed CT SAE Report Form is maintained in the investigator site file.

8.3.6. Medication Errors

Medication errors may result from the administration or consumption of the investigational products by the wrong participant, or at the wrong time, or at the wrong dosage strength.

Exposures to the investigational products under study may occur in clinical trial settings, such as medication errors.

Safety Event	Recorded on the CRF	Reported on the CT SAE Report Form to Pfizer Safety Within 24 Hours of Awareness
Medication errors	All (regardless of whether associated with an AE)	Only if associated with an SAE

Medication errors include:

- Medication errors involving participant exposure to the investigational products;
- Potential medication errors or uses outside of what is foreseen in the protocol that do or do not involve the study participant.

Such medication errors occurring to a study participant are to be captured on the medication error page of the CRF, which is a specific version of the AE page.

In the event of a medication dosing error, the sponsor should be notified immediately.

Whether or not the medication error is accompanied by an AE, as determined by the investigator, the medication error is recorded on the medication error page of the CRF and, if applicable, any associated AE(s), serious and nonserious, are recorded on an AE page of the CRF.

Medication errors should be reported to Pfizer Safety within 24 hours on a CT SAE Report Form **only when associated with an SAE**.

8.4. Treatment of Overdose

While overdose following topical administration is unlikely, there is a possibility that an excess of crisaborole may be applied. If too much crisaborole has been applied, the excess can be wiped off. Investigator should monitor the participant for any AEs/SAEs.

8.5. Pharmacokinetics

PK parameters are not evaluated in this study.

8.6. Pharmacodynamics

PD parameters are not evaluated in this study.

8.7. Genetics

Genetics (specified analyses) are not evaluated in this study.

8.8. Biomarkers

Biomarkers are not evaluated in this study.

8.9. Health Economics

Health economics/medical resource utilization and health economics parameters are not evaluated in this study.

9. STATISTICAL CONSIDERATIONS

Detailed methodology for summary and statistical analyses of the data collected in this study is outlined here and further detailed in a statistical analysis plan (SAP), which will be maintained by the sponsor. The SAP may modify what is outlined in the protocol where appropriate; however, any major modifications of the primary endpoint definitions or their analyses will also be reflected in a protocol amendment.

9.1. Estimands and Statistical Hypotheses

9.1.1. Estimands

The primary estimand of this study is the hypothetical estimand, which estimates the effect as if all participants maintain their randomized treatment. It includes the following four attributes:

- Population: Participants with mild to moderate AD in adults (cohort 1) and pediatrics (cohort 2) as defined by the inclusion and exclusion criteria and are randomized and received at least one of the investigational products;
- Variable: Change from baseline to Day 15 in lesion severity in a continuous outcome measured such as TSS, ISGA and Pruritus assessment in target lesions treated with crisaborole ointment 2% or vehicle in each regimen for each cohort;
- Intercurrent event: All efficacy data after discontinuation of treatment will not be considered;
- Population-level summary: Least-square means of intra-participant difference between crisaborole ointment 2% vs corresponding vehicle in each regimen for each cohort and pooled cohort. Difference in least-square means between crisaborole ointment 2% BID and crisaborole ointment 2% QD for each cohort and pooled cohort.

The primary and secondary efficacy endpoints will be analyzed using this estimand.

CCI

9.2. Sample Size Determination

For each cohort and for each regimen, a sample size of 16 will have at least 85% power to establish the superiority of crisaborole ointment 2% to vehicle as measured by the change from baseline in TSS between crisaborole treated lesion and the corresponding vehicle treated lesion at Day 15 using paired t -test at 0.025 (one-sided) significance level, assuming the mean of intra-participant difference is 1.8 and standard deviation is 2.2 calculated based

on the pooled results of C3291001 and AN2898-AD-202 studies. In addition, considering that the non-compliance/discontinuation rate during the treatment period is approximately 20%, approximately 20 participants will be enrolled for each regimen, and for each cohort.

In addition, for each cohort, in the inter-participant comparison between crisaborole ointment 2% BID treated lesion and crisaborole ointment 2% QD treated lesion, the sample size of 32 (16 per regimen) and 40 (20 per regimen) will result in a 2-sided 95% confidence interval width of the difference of mean for the change from baseline in TSS will be approximately 1.32 and 1.18, respectively, assuming a common standard deviation is 1.9 based on the pooled results of C3291001 and AN2898-AD-202 studies and the normal approximation.

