2.1. Study Rationale

Confirmatory evidence of efficacy and safety was provided by two well-controlled Phase 3 studies conducted in the US in AD patients 2 years of age and older. Long-term safety was evaluated in an open label study that enrolled participants from the Phase 3 studies. Based on the outcome of these studies, crisaborole ointment 2% was approved and is on US and Canada market under the tradename of EUCRISA (crisaborole) ointment, 2% twice daily (BID) indicated for topical treatment of mild to moderate AD in patients 2 years of age and older.

In Japan, phase 1 study (C3291029) was conducted and safety and tolerability crisaborole ointment 2% BID has been shown in Japanese participants. Based on this study results, it is considered that similar pharmacokinetics (PK) profile and systemic exposure were shown between Japanese and Non-Japanese participants.

In this study, two regimens of crisaborole ointment 2%, BID and once daily (QD), will be compared relative to corresponding vehicle. In addition, a descriptive comparison between crisaborole BID and crisaborole QD will be conducted to select the dose regimen for next clinical phase in each age group; adults/adolescents (12 years or older) and pediatrics (2 years to under 12 years) in Japanese AD patients.

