Secondary	
 As for the inter-participant comparison between crisaborole BID treated lesion and crisaborole QD treated lesion for each cohort, the change from baseline in TSS will be analyzed using a MMRM that includes the fixed effects of dosing regimen, visit, dosing regimen-by-visit interaction, and baseline value and an unstructured variance and covariance matrix will be used to model the dependence among the same participants across different visits up to Day 15. A MMRM analysis will be conducted including only the observed data in the model under the assumption of the MAR for the missing mechanism. For other continuous endpoints such as change from baseline in ISGA at all visits and pruritus assessment at all days, a MMRM will be applied. As for the intra-participant comparison between crisaborole treated lesion and the corresponding vehicle treated lesion for each regimen, and for each cohort, the intra-participant difference of change from baseline between crisaborole treated lesion and vehicle treated lesion, will be analyzed using a MMRM that includes the fixed effect of time point (visit or day) and an unstructured variance and covariance matrix will be used to model the dependence among the same participant across different time points (visits or days) up to Day 15. As for the inter-participant comparison between crisaborole BID treated lesion and crisaborole QD treated lesion for each cohort, the change from baseline will be analyzed using a MMRM that includes the fixed effects of dosing regimen, time point (visit or day), dosing regimen-by-time point (visit or day) interaction, and baseline value and an unstructured variance and covariance matrix will be used to model the dependence among the same participant across different time points (visits or days) up to Day 15. A MMRM analysis will be conducted including only the observed data in the model under the assumption of the MAR for the missing mechanism.

CCI

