## **6.2. Secondary Endpoint(s)**

### **6.2.1. Change from Baseline in TSS in Target Lesions at Day 15 (Comparison of Crisaborole BID vs Crisaborole QD)**

#### **6.2.1.1. Main Analysis**

- Estimand strategy: Hypothetical ([Section 2.1](#)).
- Analysis time point: Day 15.
- Analysis set: FAS ([Section 4](#)).
- Analysis methodology: For the inter-participant comparison of crisaborole BID vs crisaborole QD for each cohort, the change from baseline in TSS in target lesions between crisaborole BID and crisaborole QD up to Day 15 will be analyzed using a MMRM that includes the fixed effects of dosing regimen, visit, dosing regimen-by-visit interaction, and baseline value specified in [Section 5.2.2](#).
- Intercurrent events and missing data: All efficacy data after discontinuation of treatment will not be considered ([Section 2.1](#)). Observed data will be included in the model, and the missing values will be handled in the model, where the values are assumed to be MAR ([Section 5.3](#)).
- Reporting results:
  - Observed score: The sample size, mean, SE, standard deviation, median, Q1, Q3, minimum and maximum at baseline and post-baseline visits will be presented for each treatment.
  - Change from baseline: The sample size, mean, SE, standard deviation, median, Q1, Q3, minimum and maximum at post-baseline visits will be presented for each treatment. The least-squares mean and the corresponding SE, 95% CI for each treatment, the difference between the least-squares means of treatments and the corresponding SE, 95% CI, p-value will be presented for all post-baseline visits.

- Figures: Line plots of the mean change ( $\pm$  SE) from baseline to Day 8 and 15 for two treatments (ie, crisaborole BID vs crisaborole QD) in one figure. Figures will be developed for each cohort, separately.

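### Protocol Section 9.2 gives the half-widths of the BID versus QD confidence intervals (1.32 and 1.18) as their widths; the full widths are 2.63 and 2.36

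*Protocol*

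**What the plan says.** Protocol Section 9.2 first sizes the study on the paired crisaborole versus vehicle test, with 16 evaluable and 20 enrolled participants per regimen in each cohort. It then gives a precision statement for the between-participant comparison of BID with QD, at 16 and 20 per regimen: "2-sided 95% confidence interval width of the difference of mean for the change from baseline in TSS will be approximately 1.32 and 1.18". The assumptions follow in the same sentence: "assuming a common standard deviation is 1.9 based on the pooled results of C3291001 and AN2898-AD-202 studies and the normal approximation".

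The purpose of the comparison is set out in Protocol Section 2.1, and again in Section 4.3: "a descriptive comparison between crisaborole BID and crisaborole QD will be conducted to select the dose regimen for next clinical phase", in each age group. SAP Section 6.2.1.1 reports it formally for Total Sign Score (TSS): "the difference between the least-squares means of treatments and the corresponding SE, 95% CI, p-value will be presented for all post-baseline visits". The SAP neither repeats nor corrects the planned precision.

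**The concern.** The width of a confidence interval is the distance from its lower to its upper limit. Taken that way, 1.32 and 1.18 look too small for two groups of 16 or 20 with a standard deviation of 1.9.

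Read as written, the planned interval is the estimate ± 0.66 (16 per regimen) or ± 0.59 (20 per regimen). If the figures are really half-widths, it is the estimate ± 1.32 or ± 1.18. A reader relying on the text would expect an observed BID–QD difference of about 0.66 to exclude zero with 16 per regimen, when about 1.32 is needed. No other planned precision is stated for this comparison, so anyone judging how well the study can separate the two regimens has only this figure to go on.

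**Working it through.** **Inputs, all from Protocol Section 9.2:** two-sided 95% level (z = 1.96); common standard deviation 1.9; n = 16 or 20 per regimen; two independent groups; normal approximation.

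**Formulas:** SE = 1.9 × √(2/n); half-width = 1.96 × SE; full width = 2 × 1.96 × SE.

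| n per regimen | SE | Half-width | Full width | Stated as width |
|---|---|---|---|---|
| 16 | 1.9 × √(2/16) = 0.6718 | 1.317 | 2.633 | 1.32 |
| 20 | 1.9 × √(2/20) = 0.6008 | 1.178 | 2.355 | 1.18 |

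The stated figures match the half-widths to two decimals.

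**Other readings tried:**
- A t quantile in place of z gives half-widths of 1.372 and 1.216, and full widths of 2.744 and 2.433.
- A 90% level gives half-widths of 1.105 and 0.988.
- Taking 32 and 40 as the numbers per regimen gives full widths of 1.862 and 1.665.
- A single-mean interval with n = 16 and 20 also gives full widths of 1.862 and 1.665.
- A single-mean interval with n = 32 and 40 does have full widths of 1.317 and 1.178, because 2/√(2n) = √(2/n). This is a coincidence: the sentence concerns a difference between two regimens.

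None of these makes 1.32 and 1.18 the full width of a two-group 95% interval.

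**What would make the stated widths true, changing one input at a time:**
- Standard deviation: 1.32 / (2 × 1.96 × √(2/16)) = 0.95, and likewise 0.95 from 1.18 with n = 20.
- Participants per regimen: 2 × (2 × 1.96 × 1.9 / 1.32)² ≈ 64, and 2 × (2 × 1.96 × 1.9 / 1.18)² ≈ 80.
- Confidence level: 2Φ(0.66/0.6718) − 1 = 0.674, and 2Φ(0.59/0.6008) − 1 = 0.674, so about 67%.

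**Baseline adjustment.** The planned repeated-measures model contains "fixed effects of dosing regimen, visit, dosing regimen-by-visit interaction, and baseline value", and adjusting for baseline can narrow the interval. The documents give no correlation r between baseline and change, so a range has to be assumed. The width scales with √(1 − r²). For r from 0 to 0.5, the full width runs from 2.63 to 2.28 (n = 16) and from 2.36 to 2.04 (n = 20). Halving it needs √(1 − r²) = 0.5, that is r ≈ 0.87. The stated figures come from the unadjusted formula in any case.

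**Primary sample size.** The paired t-test with n = 16, mean difference 1.8, standard deviation 2.2 and one-sided 0.025 has 86.4% power, which agrees with the stated minimum of 85%. Also 16 / (1 − 0.20) = 20. The error does not reach this part of the section.

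**The case against.** The best defence is that this is one wrong word with little consequence. Every input stands in the same sentence, so a statistician can recover the meaning. The BID–QD comparison is secondary and called descriptive. The regimen choice can rest on the interval actually observed, not on a planning figure. No precision target for BID versus QD exists, and the number of participants comes from the paired test.

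All of that is true, and it limits the point to the stated precision. It does not make the sentence correct. Although width is sometimes used loosely for half-width, nothing here says so, and the plain reading is wrong by a factor of two.

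It would also be unfair to set the corrected widths against the 1.8-point effect assumed in the same section and conclude that precision is inadequate. That effect is a within-participant difference from vehicle, a different contrast, and whether an interval excludes zero depends on its half-width. The plan sets no expected or target BID–QD difference in TSS points, so nothing is claimed here about whether ± 1.32 or ± 1.18 is good enough.

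**Conclusion.** The concern holds. The figures 1.32 and 1.18 are correctly calculated half-widths labelled as widths; the full widths are 2.63 and 2.36 TSS points, so the stated precision is twice as good as the inputs support. This rests only on the section's own assumptions: standard deviation 1.9, equal groups of 16 or 20, the normal approximation and no baseline adjustment. It should be corrected because it is the sole planned precision for the comparison that informs regimen selection. It does not affect the sample size, the power for the primary comparison, any planned analysis or the interpretation of the intervals that will be reported.

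**What to change.** In Protocol Section 9.2, replace the phrase on interval width with: *a 2-sided 95% confidence interval half-width of approximately 1.32 and 1.18 (full width 2.63 and 2.36), respectively*. If an interpretive remark is wanted, keep it conditional: under these assumptions and without baseline adjustment, the within-cohort interval is the estimate ± about 1.2 to 1.3 TSS points.

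The change adds no participants and alters no analysis; its only effect is that the stated precision looks less favourable. Protocol Section 10.1.1 sends protocol amendments through ethics review, so a stand-alone amendment for this label would be out of proportion. It can go into the next amendment. A clarifying note in the SAP would also serve, since Protocol Section 9 and SAP Section 2 let the SAP modify what the protocol outlines.
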